APPENDIX IV - DOCUMENTATION FOR STUDY

Follow-up is required for patients from the time of randomization and will apply to all eligible patients.

This trial will use a web-based Electronic Data Capture (EDC) system for all data collection. For details of accessing the EDC system and completing the on-line Case Report Forms please refer to the “CCTG EDC Generic Data Management Guidebook” posted on the CO.26 area of the CCTG web-site (www.ctg.queensu.ca).

The electronic CRFs to be used in this trial, through the EDC system, are as follows:

| Electronic Folder | Timing | To be completed electronically | Supporting Documentation Required ¹ |
|---|--|--|--|
| Eligibility Checklist | | At the time of randomization | 
 • consent form² |
| Baseline Report | | Within 2 weeks of randomization | 
 • relevant pathology report(s) • RAS reports • relevant operative report(s) • relevant radiology reports (including CT/MRI abdomen/pelvis, CT/MRI chest, chest x-ray) • tumour measurement worksheet • ECG report |
| Correlative Studies Report (Tumour and Blood) | Continuous running-log folder See Section 5.0 | Information pertaining to tumour tissue submission must be completed as soon as possible after randomization, and tissue submitted within 4 weeks of randomization. | 
 • Consent form² • Diagnostic pathology report (for tumour tissue only) |
| | | Information pertaining to baseline/pretreatment blood collection for correlative studies (i.e. whole blood, plasma, serum) must be completed within 2 weeks of randomization. | |
| | | Information pertaining to post randomization blood collection samples (i.e. whole blood, plasma, serum) for correlative studies and banking should be completed within 2 weeks after collection of blood specimens. | |
| Concomitant Medication Report | Continuous running-log folder | | |
| Best Supportive Care Report (Arm 1 only) | Every 4 weeks (28 days) until objective progression | Within 2 weeks of the end of each reporting period | 
 • If available/applicable: • CT/MRI abdomen/pelvis report • CT/MRI chest • other radiology reports • tumour measurement worksheet • ECG report |

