| Treatment Report (Arm 2 only) | Every 4 weeks (28 days) while patient is on protocol treatment | Within 2 weeks of the end of each 4 week reporting period | If available/applicable: 
 • CT/MRI abdomen/pelvis report • CT/MRI chest • other radiology reports • tumour measurement worksheet • ECG report |

table continues on next page ...

| Electronic Folder | Timing | To be completed electronically | Supporting Documentation Required ¹ |
|--|---|---|--|
| End of Treatment Report(Arm 2 only) | As soon as permanent off treatment status is confirmed. | Within 2 weeks of end of treatment | |
| 4-Week Post-Treatment Follow-Up Report (Arm 2 only) | 4 weeks from the date of last infusion | Within 2 weeks of the 4-week post treatment follow up visit | 
 • relevant radiology reports |
| Follow-up Report ³ (Arm 2 only) | Every 4 weeks (28 days) until objective progression | Within 2 weeks of follow-up visit | If available/applicable: 
 • CT/MRI abdomen/pelvis report • tumour measurement worksheet • CT/MRI chest report • other radiology reports • ECG report |
| Short Follow-up Report | Every 12 weeks after objective disease progression | Within 2 weeks of follow-up visit | |
| Relapse/Progression Report | Upon the patient's objective disease progression / relapse | Within 4 weeks of confirmation | 
 • relevant radiology, operative and pathology reports |
| Death Report | Upon patient's death | Within 4 weeks of patient death | 
 • autopsy/post-mortem report, if performed |
| Serious Adverse Event (SAE) Report ⁴ | Within 24 hours of event At time of event and reported to CCTG | Within 1 working day ⁴ | |
| Minimal Follow-up Report ⁵ | Annual | Within 6 weeks of contact | If available/applicable: 
 • autopsy report • CT/MRI report |

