4.3 Safety

The safety endpoints are serious and non-serious adverse events (clinical and laboratory), laboratory parameters, dosing data (including dose interruptions, total delivered dose and dose modifications) and reasons off treatment.

5. Sample Size and Power

The primary objective of this study is to assess the additional effect of durvalumab and tremelimumab to best supportive care by comparing overall survival (OS) between Durva+Treme and BSC arms among all randomized patients. It was calculated that with a 2-sided alpha of 10%, a total of 180 patients with 150 events (deaths) would be required to provide 80% power to detect a 2.4 month difference in median survival (a hazard ratio of 0.65) between the two treatment arms assuming a median survival of 4.5 months for the BSC alone arm. The final analysis will be conducted after at least 150 events have been recorded. It is estimated that 180 patients accrued over 18 months and followed for 6 months will be required to reach the necessary number of events.

6. Data Set Descriptions

Three types of analysis samples will be used:

All Randomized Patients:

All patients who have been randomized in the study with the treatment arm being as randomized.

Response-Evaluable Patients:

All patients who have received at least one cycle of therapy and have their disease re-evaluated will be considered evaluable for response (exceptions will be those who exhibit objective disease progression prior to the end of cycle 1 who will also be considered evaluable).

All Treated Patients:

All patients on Durva+Treme who received at least one dose of durvalumab and tremelimumab and on BSC who had at least one Best Supportive Care Report.

Patients randomized to BSC who have received at least one dose of durvalumab and tremelimumab on study (from Cancer Treatment Section of Best Supportive Care Report) will be grouped with patients randomized to Durva+Treme in analyses of safety.

7. Statistical Analysis

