7.7 Safety

The safety analyses will be based on the All Treated population defined in Section 6. Adverse events and laboratories are graded and categorized using the CTCAE v4.0 criteria except where CTCAE grades are not available.

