7.7.1 Adverse Events

Adverse events will be recorded on the CCTG toxicity/adverse event-intercurrent illness case report form. Events reported on Treatment Report or 4-Week Post-Treatment Follow-Up Report for patients on the Durva+Treme arm will be defined as adverse events on Durva+Treme; Events reported on any case report forms except Form 1 will be summarized separately for patients on both arms as overall adverse events during the (whole) study.

Drug related adverse events are those events with a relation to protocol therapy of 3=possible, 4=probable or 5=definite.

Severe adverse events are those events reported with a CTCAE Grade of 3 or higher.

Comparisons between treatment arms on overall adverse events (any vs. other, severe vs. other) will be carried out using a two sided Fisher's exact test at an alpha level of two-sided 10%.

The following variables are summarized. Tabulations of overall adverse events will be presented by treatment group.

- Adverse events on Durva+Treme: worst CTCAE grade per patient (**Table 42**)
- Severe adverse events on Durva+Treme: worst CTCAE grade per patient (**Table 43**)
- Drug related adverse events on Durva+Treme: worst CTCAE grade per patient (**Table 44**)
- Overall adverse events: worst CTCAE grade per patient (**Table 45**)
- Severe overall adverse events: worst CTCAE grade per patient (**Table 46**)

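### BSC patients regrouped to Durva+Treme for safety carry their pre-dose events with them into the overall tables, because the SAP sets no cut at first dose

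*SAP*

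**What the plan says.** SAP Section 6 defines the All Treated set. A BSC patient who has had at least one dose of durvalumab and tremelimumab, identified as "on study (from Cancer Treatment Section of Best Supportive Care Report", "will be grouped with patients randomized to Durva+Treme in analyses of safety". SAP 7.7 applies this to everything that follows: "The safety analyses will be based on the All Treated population defined in Section 6".

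SAP 7.7.1 then sorts adverse events by the form they were reported on, not by date:

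- **Overall events:** "Events reported on any case report forms except Form 1 will be summarized separately for patients on both arms as overall adverse events". Any and severe overall events are compared between arms by a two-sided Fisher's exact test at 10%.
- **On-treatment events:** "Events reported on Treatment Report or 4-Week Post-Treatment Follow-Up Report for patients on the Durva+Treme arm will be defined as adverse events on Durva+Treme".

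SAP 7.7.2 treats laboratory data in the same way. The overall tables take every result after baseline, and the on-treatment tables take the same two forms.

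Protocol Appendix IV marks the Treatment Report ("Every 4 weeks (28 days) while patient is on protocol treatment") and the 4-Week Post-Treatment Follow-Up Report as Arm 2 only. It marks the Best Supportive Care Report ("Every 4 weeks (28 days) until objective progression") as Arm 1 only.

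**The concern.** Grouping by treatment received is meant to line events up with exposure. This rule lines patients up with exposure but leaves their events unsorted. A BSC patient may have had weeks of disease-related events before a first dose, and all of them would be tabulated in the drug column and would disappear from the BSC column. Toxicity of the combination is a secondary objective, and the overall events are the ones formally tested between arms.

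The same patient also has no form that feeds the on-treatment tables, so a genuine reaction after dosing would be missing from Tables 42-44, where a reader would look for it. Pre-exposure events are thus counted as drug-arm events in one set of tables, while post-exposure events are absent from the other.

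**Working it through.** The plan gives no figure on this point, so there is none to reproduce. The check follows one regrouped patient through the definitions and then shows how far counts could move under stated assumptions.

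**Tracing the patient**

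1. *Entry.* The trigger is a record "from Cancer Treatment Section of Best Supportive Care Report". That form ends at objective progression, so the rule reaches only patients given the drugs before progression.
2. *Overall tables (45, 46, 48, 50, 52, 54).* Protocol 5.1 collects Arm 1 adverse events from randomization to objective progression. SAP 7.7.1 takes every form except Form 1, which I take to be the baseline form. SAP 7.7.2 takes every post-baseline laboratory value. Neither has a start-date condition, so pre-dose data go to Durva+Treme.
3. *On-treatment tables (42-44, 47, 49, 51, 53).* These need a Treatment Report or a 4-Week Post-Treatment Follow-Up Report. An Arm 1 patient has neither, so post-dose events cannot enter.
4. *Possible safeguard.* Protocol 8.1.1 makes patients evaluable for adverse events from first treatment. The SAP does not carry this into its table definitions.

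**Overall tables: illustration**

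Arm sizes of 120 and 60 are from SAP 2.1. Everything else is assumed: severe events in 30% of Durva+Treme (36/120) and 20% of BSC (12/60) as randomized; k regrouped patients, of whom x had a severe pre-dose event; and no severe post-dose events among them. Under the SAP rule the counts become (36+x)/(120+k) and (12-x)/(60-k).

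| k | x | Durva+Treme | BSC | Fisher p |
|---|---|---|---|---|
| 0 | 0 | 36/120 = 30.0% | 12/60 = 20.0% | 0.210 |
| 3 | 1 | 37/123 = 30.1% | 11/57 = 19.3% | 0.149 |
| 3 | 3 | 39/123 = 31.7% | 9/57 = 15.8% | 0.030 |
| 6 | 1 | 37/126 = 29.4% | 11/54 = 20.4% | 0.270 |
| 6 | 6 | 42/126 = 33.3% | 6/54 = 11.1% | 0.002 |

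The rows with x = k are extremes. The shift can go in either direction.

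**On-treatment tables: only if regrouped patients are in N**

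The numerator is fixed, so each rate is multiplied by 120/(120+k). This is 0.992, 0.976 and 0.952 for k = 1, 3 and 6. An assumed 40% rate would show as 39.7%, 39.0% or 38.1%. If these patients are not in N, the factor is 1.

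**The case against.** **The trigger is narrow.** The protocol plans no crossover. Drugs given after progression would be reported on the Short Follow-up Report, which does not trigger the rule. The number regrouped may well be zero. This stands, and it limits the importance of the point, but it does not make the rule correct when it is used.

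**Whole-patient grouping is sometimes right.** A BSC patient given the drugs from the outset through an allocation error should be counted wholly under Durva+Treme. That also stands. A first-dose cut gives nearly the same result for such a patient, so the two do not conflict.

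**A reader might infer that on-treatment and drug-related rates are diluted.** The documents do not establish this. SAP 2.2 defines the Durva+Treme Arm by allocation, SAP 7.7.1 and 7.7.2 limit on-treatment events to patients on that arm, and the on-treatment tables carry a matching label. On that reading regrouped patients are absent from N and nothing is diluted. SAP 7.7 read with Section 6 points the other way, and Table 45, an overall table, carries the same label. The label is ambiguous. What holds on either reading is that post-dose events cannot appear.

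**A reader might also infer that BSC loses its fitter patients.** Neither document says anything about who would be given the drugs, so this has no support.

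**Splitting a patient at first dose would put one person in both columns.** Fisher's exact test needs each patient in one group only. This objection is sound, and it shapes the fix.

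**Conclusion.** The point holds for the overall tables. As written, pre-exposure adverse events and laboratory values of a regrouped BSC patient are reported as Durva+Treme data and removed from BSC, and the adverse events enter the formal comparison. For the on-treatment tables, post-dose events are omitted, and the make-up of N is unclear.

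The size cannot be fixed from the documents, because the number of regrouped patients and all event rates above are assumptions. With none, the effect is nil. With a handful, rates move by at most a few points in Durva+Treme and by more in the smaller BSC group. The test result could cross the 10% level only in unfavourable configurations such as k = x = 3. The primary survival analysis is by randomized arm and is not touched. This is a minor correction, worth making because it is cheap.

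**What to change.** In SAP Section 6, add that for regrouped BSC patients only adverse events and laboratory values on or after the first dose count under Durva+Treme, and that pre-dose events are listed separately as BSC-period events. For the Fisher comparison, keep each patient in one group only. State that regrouped patients are excluded from N in Tables 42-44, 47, 49, 51 and 53, with their post-dose events listed separately.

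The cost is a small amount of programming and one extra listing. Neither document shows that onset dates are captured on the Best Supportive Care Report. Where they are not, the 4-week reporting period can place an event before or after first dose, with some imprecision in the period containing that dose.

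The change corrects the drug column but does not restore the BSC column. In the k = x = 3 example the counts become 36/123 = 29.3% vs 9/57 = 15.8% (Fisher p=0.064), because the three patients have still left BSC. The separate listing is therefore needed, so that a reader can see what was removed.

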7.1 General Methods

All comparisons between treatment arms will be carried out using a two-sided test at an alpha level of 10% unless otherwise specified.

When appropriate, discrete variables are summarized with the number and proportion of subjects falling into each category, and compared using Fisher's exact test. Continuous and ordinal categorical variables are summarized using the mean, median, standard error, minimum and maximum values and when appropriate, compared using the Wilcoxon test. All confidence intervals are computed based on normal approximations except those for rates, which will be computed based on the exact method.

Time to event variables are summarized using Kaplan-Meier plots. Primary comparisons of the treatment groups are made using the stratified log-rank test. Primary estimates of the treatment differences are obtained with the hazard ratios and 90% confidence intervals from stratified Cox regression models using treatment arm as the single factor.

Percentages given in the summary tables will be rounded and may therefore not always add up to exactly 100%. Listings, tabulations, and statistical analyses will be carried out using the SAS (Statistical Analysis System, SAS Institute, North Carolina, USA) software.

Unless otherwise specified, date of randomization and stratification factors will be taken from the Centralized Randomization File.

Baseline evaluations will be those collected on Eligibility Checklist and Baseline Report and closest to, but no later than, the first day of study medication for treated subjects and closest to, but no later than, the date of randomization, for subjects who were randomized but who never received treatment.

Laboratory results, adverse events, and other symptoms are coded and graded using the Common Terminology Criteria for Adverse Events (CTCAE v4.0).

7.2 Data Conventions

When converting a number of days to other units, the following conversion factors will be used:

1 year = 365.25 days

1 month = 30.4375 days

When either day or month of a date is missing, the missing day and/or month will be imputed by the midpoint within the smallest known interval. For example, if the day of the month is missing for any date used in a calculation, the 15th of the month will be used to replace the missing day. If the month and day of the year are missing for any date used in a calculation, the first of July of the year will be used to replace the missing date.

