2.1 Study Design

Study CCTG CO.26 is a multi-centre, open-label, randomized phase II trial of durvalumab and tremelimumab combined with best supportive care *versus* best supportive care alone (where best supportive care is defined as those measures

designed to provide palliation of symptoms and improve quality of life as much as possible) in patients with refractory, advanced colorectal carcinoma. Patients are stratified by ECOG performance status (0 vs. 1) and site of tumour (right colon vs. transverse colon vs. left colon vs. rectum vs. unknown) prior to randomization. This study is conducted by CCTG with support from AstraZeneca. CCTG Case Report Forms (CRFs) are used and the database are maintained by CCTG.

A total of 180 patients would be enrolled (120 on Durva+Treme and 60 on BSC). The final analyses will be performed by CCTG when the required number of deaths (150) is recorded. This analysis plan describes the analyses performed at the completion of the study.

This study was activated on August 10, 2016 and closed to randomization of patients on June 29, 2017 after 180 patients were randomized. The CCTG Data Safety Monitoring Committee has been reviewing safety data every six months (usually at the time of the bi-annual CCTG Spring and Fall meetings) and as otherwise required. These analyses have been prepared by a CCTG/Queen's Senior Biostatistician.

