7.6 Efficacy

7.6.1 Overall survival

For all randomized patients, survival is calculated from the day of randomization (as recorded in Centralized Randomization File) to death (Date/Cause of Death Section of Death Report). For alive patients, survival is censored at the last day the patient is known alive (LKA) as the last recorded date known alive (Date of Attendance/Last Contact on Best Support Care Report, 4-Week Post Treatment Report, Follow-up Report, Short Follow Up Report, and Minimal Follow-up Report; or last date of infusion of durvalumab or tremelimumab in Treatment Report). Survival time (in months) is defined as

$$[(\text{date of death or LKA} - \text{date of randomization}) + 1]/30.4375.$$

A frequency table for the number of patients who died and cause of death in each treatment arm will be provided (**Table 32**). Kaplan-Meier curve for proportions of survival in each treatment arm will be displayed (**Figure 2**).

The comparison of overall survival between the two treatment arms is the primary objective of this study. The primary analysis will be the log-rank test (**Table 33**) stratified by the factors coded as:

Stratification Factors (at randomization)

Performance status	1 = ECOG 0	0 = ECOG 1
Site of tumour	1=right colon; 2=transverse colon; 3=left colon; 4=rectum; 5=unknown	

The hazard ratio of durvalumab and tremelimumab combined with best supportive care (ARM 2) over best supportive care alone (ARM 1) and two-sided 90% CI will be calculated (**Table 33**) based on the Cox regression model stratified by above stratification factors, and with treatment arm coded as ARM 2=1 and ARM 1=0. The 90% confidence intervals for the median survival will be computed using the method of Brookmeyer and Crowley [2].

In order to assess the influence of the potential prognostic factors shown and coded below on the comparison of survival between treatment arms, a stratified Cox regression model will be used with all variables (treatment arm and prognostic factors) included to estimate hazard ratios and 90% confidence intervals (**Table 33**).

Prognostic factors (at baseline)

Gender	0 = Female	1 = Male
Age	0 = ≥ 65	1 = < 65
Number of organ sites	0 = > 2	1 = ≤ 2
Presence of liver metastases	0 = Yes	1 = No

No interactions will be considered in the model.

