7.6.3 Progression-free Survival

Progression-free survival (PFS) will be calculated for all patients from the day of randomization until the first observation of disease progression (date of objective relapse or progression of Relapse/Progression Report) or death due to any cause (recorded in Date/Cause of Death Section of Death Report) as the (difference+1).

If a patient has not progressed or died, PFS will be censored on the date of last disease assessment defined as the earliest test date of target lesion or non-target lesions (if patient has no target lesions), whichever is latest.

A frequency table will be provided describing progression and censoring as follows (**Table 35**):

- Number of patients who progress (documented progression, death without documented progression)
- Number of patients censored (alive and not progressed)

Analyses for PFS will be similar to that for overall survival as previously described. A Kaplan-Meier curve for PFS in each treatment arm will be displayed (**Figure 3**). In the primary analysis, median PFS for the two treatments will be compared using the stratified log-rank test (**Table 36**). A stratified Cox regression model will estimate the durvalumab and tremelimumab combined with best supportive care (ARM 2) over best supportive care alone (ARM 1) PFS hazard ratio and 90% C. I. (**Table 36**). In addition, a stratified Cox regression model adjusted for covariates will be applied to verify the impact of the prognostic factors on the treatment effect (**Table 36**).

Coding for treatment arm, stratification variables and prognostic factors is identical to that presented in **Section 7.5.1**.

Some patients received other anti-cancer therapy before progression or death. Sensitivity analyses will be performed by censoring those who have received anti-cancer therapy prior to documentation of disease relapse/progression or death on the earliest date cancer treatment began or treating them as having PFS events at the earliest date when the treatment began.

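### The SAP's partial-date rule has no lower bound, so an imputed death or progression date can fall before randomization or before a documented contact alive

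*SAP*

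**What the plan says.** The general rule in SAP 7.2 is that "the missing day and/or month will be imputed by the midpoint within the smallest known interval". Two worked cases follow. In the first, where only the day is unknown, "the 15th of the month will be used to replace the missing day". Its scope is not limited to particular variables: it operates "if the day of the month is missing for any date used in a calculation". The second, for month and day both missing: "the first of July of the year will be used to replace the missing date". The section mentions no other date that the imputed value must respect.

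SAP 7.6.1 states that "survival is calculated from the day of randomization (as recorded in Centralized Randomization File) to death", adds one day and divides by 30.4375 to give months. SAP 7.6.3 builds PFS in the same way, as the difference plus one. Neither section sets a minimum. For patients without a PFS event, "PFS will be censored on the date of last disease assessment"; nothing is said about a patient whose only assessment is the baseline scan. SAP 2.1 gives the accrual window: "This study was activated on August 10, 2016 and closed to randomization of patients on June 29, 2017".

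**The concern.** A survival time that starts at randomization cannot be zero or negative under the SAP's plus-one convention, and a patient cannot die before a visit that he or she attended. The rule in 7.2 permits both results for deaths and progressions with partial dates. It also governs the start date of other anti-cancer therapy, which the two PFS sensitivity analyses in 7.6.3 use as a censoring or event date.

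OS and PFS are to be analysed in all randomized patients. The SAP does not say what happens to a non-positive time. The record would be dropped, which loses an event, or kept at a false time, or repaired by a rule chosen after the data are in hand, in an open-label trial. Post-progression follow-up may be by telephone (Protocol 5.1 and 5.2), so partial dates are possible.

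**Working it through.** **Inputs.** Imputation values: SAP 7.2. Time = end date - randomization date + 1 day: SAP 7.6.1 and 7.6.3. Accrual 10 August 2016 to 29 June 2017: SAP 2.1. Contact every 4 weeks before progression and every 12 weeks after it: Protocol 5.1, 5.2 and Appendix IV. Baseline imaging up to 28 days before randomization: Protocol 4.1.10.

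**The plan's own figure.** Schoenfeld's formula with 2:1 allocation, HR 0.65, two-sided 10% alpha and 80% power gives (1.645 + 0.842)² / [(2/3)(1/3)(ln 0.65)²] = 6.18 / 0.0412 = 150 deaths, as planned. The date rule does not enter this calculation.

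**1. Year-only 2016 event date.** The imputed date is 1 July 2016; 10 August - 1 July = 40 days before activation.
- Randomized 10 August 2016: -40 + 1 = -39 days (-1.28 months).
- Randomized 31 December 2016: -183 + 1 = -182 days (-5.98 months).

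A patient with an event in 2016 was randomized in 2016, so every such time is negative. That part of the window is 144 of 324 accrual days (44%), a share of days and not of patients or events.

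**2. Year-only 2017 event date.** The imputed date is 1 July 2017. For the latest possible entry, 29 June 2017, the time is 2 + 1 = 3 days, so it is never negative. It can still precede a contact alive later in 2017, by up to 183 days (1 July to 31 December).

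**3. Day missing, event in the month of randomization.** With entry on day r, the time is 15 - r + 1 = 16 - r days: zero for r = 16, negative from r = 17, and -15 for r = 31. Entry on the 17th or later covers 157 of 324 accrual days (48%).

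**4. Day-missing death imputed before a known contact.** Assume a 30-day month, a death day equally likely to be 1 to 30, and a gap since last contact equally likely to be 0 to L - 1 days. The last contact falls after the 15th when the gap is less than death day - 15. For death days 16 to 30 that is 1, 2, ..., 15 favourable gaps, 120 in all.
- L = 28 (4-weekly contact): 120 / (30 × 28) = 14%.
- L = 84 (12-weekly contact): 120 / (30 × 84) = 5%.

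The contradiction is at most 31 - 15 = 16 days.

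**5. How many deaths could be exposed.** Assume uniform accrual of 180 patients and exponential survival, with a median of 6.9 or 4.5 months applied to everyone.
- Deaths in 2016: 180 × 0.091 = 16 to 180 × 0.130 = 23.
- Deaths in the month of randomization after entry on the 17th or later: 180 × 0.0122 = 2 to 180 × 0.0185 = 3.

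These are ceilings. Only deaths that also have a partial date of the relevant kind are affected.

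**6. PFS censored at a baseline scan k days before randomization.** The time is 1 - k days: +1 at k = 0, 0 at k = 1, -13 at k = 14, -27 at k = 28. A patient censored at or before day 1 is in no later risk set, so dropping the patient and censoring at day 1 give the same log-rank statistic and hazard ratio, barring an event on day 1.

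**The case against.** The strongest reply is that the governing rule is the midpoint of the smallest known interval, with the 15th and 1 July only as examples. If randomization or last contact is known, the interval could be read as already bounded by it. That reading is possible, but both examples take the whole calendar month or year and no bounding date is named. A programmer following the text would use the 15th and 1 July.

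The second reply is that partial event dates should be rare. Deaths have their own report with a date section, due within weeks, and progression reports need supporting radiology. This stands, and it limits the size of the point.

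Several stronger readings are tempting and are not supported:
- **Every year-only 2016 date fails.** It does not. The rule also covers historical dates such as first diagnosis (SAP 7.4.1), for which 1 July 2016 causes no difficulty.
- **Censoring dates also make OS negative.** They do not. The last date known alive comes from post-randomization forms or infusions, so negative OS arises only from imputed event dates.
- **About 14% of day-missing deaths precede last contact.** That holds only for 4-weekly contact up to death; after progression contact is 12-weekly and the figure is about 5%.
- **The baseline-scan gap biases the PFS comparison.** Step 6 shows that it affects only the displayed numbers and times.

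**Conclusion.** The point holds for post-randomization event dates. Applied as written, SAP 7.2 can give OS or PFS times of -39 to -182 days for a year-only 2016 date and 0 to -15 days for a day-missing date in the month of randomization. It can also place a death before a documented contact alive. These results follow from the SAP's own rules and dates. The 5% to 14% range rests on the assumed contact intervals and uniform timing, and the exposure counts rest on uniform accrual and exponential survival.

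The number of partial dates is not given and is probably small. A reader might infer that the primary OS result is compromised; the documents do not show that, and the planned 150 deaths and 80% power are unaffected. The case for acting is that a written rule gives impossible values on the primary endpoint and is easily corrected before analysis.

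**What to change.** Add to SAP 7.2, for post-randomization dates only (death, progression, start of other anti-cancer therapy): the imputed date is the midpoint of that part of the known month or year which lies
- on or after the latest date it must follow: randomization; for death, also the last date known alive; for progression, also the last progression-free assessment; and
- on or before the earliest date it must precede: death or data cut-off.

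Historical dates such as first diagnosis keep the current rule, capped at randomization. The restriction matters, because a bound written for all imputed dates would wrongly push diagnosis dates past randomization.

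Illustration: for randomization on 10 August 2016, last known alive on 5 October 2016 and a year-only 2016 death, the interval is 5 October to 31 December (87 days). Its midpoint is 17 November 2016, so OS is 99 + 1 = 100 days instead of -39.

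Optional housekeeping in SAP 7.6.3: censor PFS at day 1 for a patient with no event and no post-baseline assessment. This keeps the reported N and times valid and does not change the log-rank test or hazard ratio.

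The cost is a few sentences and simple programming. Sample size, event target, power and alpha do not change.
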